HSS COVID-19 Antibody Serology Among Surgeons & Anesthesiologists

NCT04389294

DATE: October 15, 2020

Study Design and Setting

A cross-sectional study of the seroprevalence of SARS-CoV-2 IgG antibodies among surgeons

and anesthesiologists, with a survey assessing the presence of symptoms and risk factors

associated with COVID-19 illness. The study was conducted at Hospital for Special Surgery,

approved by the hospital's Institutional Review Board, and registered at ClinicalTrials.gov

(NCT04389294). All participants provided written informed consent.

Hospital for Special Surgery is an orthopedic surgery specialty hospital in New York City. Prior

to March 17, 2020 the hospital functioned as a comprehensive musculoskeletal care center.

After March 17, 2020, the hospital was converted into a designated COVID-19 care facility and

all elective surgical procedures were postponed. 13,14 Surgeons and anesthesiologists provided

emergency orthopedic surgical care for COVID-19-positive and -negative patients and were

additionally re-deployed from their usual roles to care for COVID-19 positive patients on the

wards and Intensive Care Units (ICU). In parallel, the institution developed and implemented

new local policies for telehealth, PPE, and infection control practices across all clinical

settings. 13-14 These processes were fully implemented by early April, 2020.

Recruitment and participants

A recruitment email was sent to all attending surgeons, anesthesiologists, and trainees in both

departments (orthopedic surgery fellows, anesthesiology fellows and orthopedic surgery

residents) as identified via an institutional listsery. An electronic survey assessing COVID-19

illness and risk factors associated with SARS-CoV-2 exposure was provided, together with an invitation to self-schedule an appointment for SARS-CoV-2 serology testing. Inclusion criteria were defined as: a positive response to the recruitment invitation, completion of the survey, and/or scheduling an appointment for serology testing. Only those participants who completed both the survey and serology testing were included in the analyses. Participation was open between May 6, 2020 and June 5, 2020. A deadline was imposed for completing both elements (June 12, 2020).

Survey and SARS-CoV-2 IgG antibody testing

The survey retrospectively assessed demographics and factors of interest which occurred between January 1, 2020 – May 5, 2020 (Figure 2). The survey included 19 questions, separated into 3 domains: 1) demographics and co-morbidities, 2) practice role, residential location, working patterns before and after March 16, 2020, mode of commuting to work, and 3) COVID-19-like illness, specific symptoms, prior testing, and known close contacts with confirmed COVID-19 illness and their relationship to the participant.

Whole blood samples were obtained and tested for IgG antibodies to SARS-CoV-2, according to the manufacturer's instructions (Abbott Laboratories, ARCHITECT SARS-CoV-2 IgG. H14806RO1).¹⁵ In studies of performance evaluation, the specificity of the assay was reported to be between 99.4–100% and sensitivity between 94.0–100% at 14 or more days after symptom onset.¹⁵⁻¹⁷

Outcomes and measurement

The primary outcome was defined *a priori* as the period prevalence of SARS-CoV-2 IgG antibodies by serology testing and the association with COVID-19 illness reported in the survey.

Secondary outcomes included differences in the remaining survey responses between IgG antibody-positive and -negative participants. These included demographics, comorbidities, practice patterns, professional role, training status, mode of commuting to work, known close contacts with confirmed COVID-19 and relationship, and prior SARS-CoV-2 testing.

Blinding

Due to the nature of the principle data collection tool (survey-based) participant blinding was not feasible. However, to minimize reporting bias – which may have been affected by knowledge of antibody status –the survey was sent in advance of serology testing. The research assistants responsible for data collection were blinded to individual serology testing results, and participants were advised they could check the results of their serology independently by contacting the hospital's Occupational Health Department.

Statistical Analyses

The period prevalence of SARS-CoV-2 IgG is expressed as a % of the total sample who met criteria for inclusion in the final analysis. Continuous variables are summarized as median (IQR) or mean (SD). Categorical variables are summarized as counts (%). The association between positive COVID-19 symptoms and SARS-CoV-2 IgG antibody status was measured by χ^2 testing. Univariate exact logistic regression analysis was conducted to estimate the odds ratio (95% CI) of differences on variables of interest between antibody-positive and -negative participants. For all tests, the α was set at 0.05. Statistical analysis was performed using SAS (version 9.4. SAS Institute, Cary, NC).

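### Does the gap between the May 5 end of the survey look-back and blood draws as late as June 12 call for a timing check on the illness–IgG association?

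*Combined protocol and SAP*

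**What the plan says.** Survey and SARS-CoV-2 IgG antibody testing fixes the look-back: "The survey retrospectively assessed demographics and factors of interest which occurred between January 1, 2020 – May 5, 2020". The same section quotes the assay's "sensitivity between 94.0–100% at 14 or more days after symptom onset" and gives no figure for shorter intervals.

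Recruitment and participants sets the dates: "Participation was open between May 6, 2020 and June 5, 2020" and "A deadline was imposed for completing both elements (June 12, 2020". Participants were invited to "self-schedule an appointment for SARS-CoV-2 serology testing". Entry to the analysis requires a completed survey and a completed serology test, with no condition on the time between onset and draw.

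Outcomes and measurement makes the primary outcome the period prevalence of IgG together with "the association with COVID-19 illness reported in the survey". Under Statistical Analyses, "The association between positive COVID-19 symptoms and SARS-CoV-2 IgG antibody status was measured by" a chi-square test. No restriction, stratification or sensitivity analysis by draw date is described.

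**The concern.** The two variables in the primary association cover different periods. Recorded illness stops at May 5, whereas IgG reflects infection up to a draw that may be more than five weeks later. Two errors can follow.

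- **Early draws.** A participant whose illness began between April 23 and May 5 could be drawn before day 14, outside the interval for which sensitivity is quoted. If sensitivity is lower there (an inference, since the documents do not say), some ill, infected people are counted as IgG-negative.
- **Late infections.** A participant who falls ill after May 5 and has seroconverted by the draw is IgG-positive with no recorded illness.

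Both would probably pull the association toward the null, and the second would inflate the share of IgG-positive people who appear to have had no illness. Because the association is part of the primary outcome, it is reasonable to ask whether a timing-restricted analysis is needed.

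**Working it through.** The plan states no sample size or expected rate, so there is no figure of its own to reproduce. The check is date arithmetic on the stated windows, followed by an illustration on assumed rates.

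**Dates (from the documents; May 6 as first draw is inferred from the opening of participation)**

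- Look-back January 1 to May 5: 126 days. Draw dates May 6 to June 12: 38.
- A May 6 draw reaches day 14 only for onsets up to April 22, leaving 13 onset days (April 23 to May 5) short. The count falls by one per day to 1 on May 18 and 0 from May 19.
- Short pairs: 13 + 12 + … + 1 = 91. All pairs: 38 × 126 = 4,788. Share: 91 / 4,788 = 1.9%, if draws and onsets are evenly spread.
- Days after May 5 and before the draw: 0 (May 6) to 37 (June 12), mean 18.5.

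**Base table (assumed)**

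Per 100 participants: prevalence 10%, illness in 60% of positives and 20% of negatives. That is 6 ill and 4 not ill among positives, 18 and 72 among negatives.

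- OR = (6 × 72) / (4 × 18) = 6.0
- Chi-square = 100 × (432 − 72)² / (10 × 90 × 24 × 76) = 7.89

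**Early error**

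Suppose 2% of ill infected people are drawn early and every one tests negative, which is the harshest assumption about sensitivity. Then 0.12 moves from ill-positive to ill-negative.

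- OR = (5.88 × 72) / (4 × 18.12) = 5.84
- Prevalence 9.88%, chi-square 7.58

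Putting every draw on May 6 raises the share to 13 / 126 = 10.3% and gives OR 5.20. This is not a ceiling, because onsets are still spread evenly; clustering in late April would raise it.

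**Late error**

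Let late infections be a share x of positives, with recorded illness at the 20% background rate. Illness among positives is then 0.60(1 − x) + 0.20x, and the odds in negatives are 18 / 72 = 0.25.

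- x = 1%: 0.596, OR = (0.596 / 0.404) / 0.25 = 5.90
- x = 5%: 0.58, OR = (0.58 / 0.42) / 0.25 = 5.52

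Late cases come out of the negatives, so positives rise to 10 / 0.95 = 10.53 per 100. At x = 5% the table is 6.11 and 4.42 against 17.89 and 71.58, with chi-square 7.46. The documents give no incidence after May 5. Study Design and Setting says of the new telehealth, PPE and infection-control policies that "These processes were fully implemented by early April, 2020", which is compatible with few late cases but does not establish it.

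**What a restriction to draws from May 19 would show**

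- With even draws, 25 of 38 dates remain (66%). The standard error of log OR grows by √(38 / 25) = 1.23.
- Pooled standard error: √(1/6 + 1/4 + 1/18 + 1/72) = 0.697, giving a 95% interval of 1.53 to 23.53. Restricted: 0.697 × 1.23 = 0.860, giving 1.11 to 32.35.
- The early-error shift to be detected is ln(6.00 / 5.84) = 0.027, about 3% of the restricted standard error.
- Post-window days now run from 13 to 37, mean 25.0 instead of 18.5, so average exposure to the late error lengthens.

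**The case for a change.** The strongest case for acting is that the mismatch sits in the primary outcome, no passage deals with it, and a check looks cheap. Sending the survey ahead of serology guards against reporting bias but not against either timing error. The shift also depends on the assumptions. With 300 participants, 10% infected, illness in 75% of infected and 15% of others, sensitivity 97% from day 14 and 50% before, and specificity 99.7%, the OR falls from 15.4 to 14.3 if 10% of ill infected people are drawn early. It falls to 10.9 if 10% of infected illnesses fall after May 5, and to 10.1 with both.

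The facts and the direction stand, and the late error could matter more than the early one. But the larger shift comes from assuming 10% late illness, which no passage supports, and even then the association is weakened, not reversed. The proposed check also fails against that error: dropping early draws leaves late infections in and raises their share of exposure time. Draw dates were self-selected, possibly by people who had been ill, so a difference from the pooled result could not be put down to misclassification.

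A check based on onset dates would be better aimed, but the survey items and Figure 2 are not shown, so whether onset was recorded is unknown. A minimum onset-to-draw interval also has no meaning for participants without symptoms, who must stay in a prevalence estimate.

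A small sample could put the test near its threshold: with 50 participants and 5 positives, the same rates give chi-square 3.95 with no error and 3.79 with 2% early. The smallest expected cell there is 5 × 12 / 50 = 1.2, and Fisher's exact test on the error-free table (3 and 2 against 9 and 36) already gives p = 0.08. That result reflects sparse data, not draw timing.

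**Conclusion.** The observation is accurate, but it does not call for a change. A fixed look-back ending the day before recruitment opened is a fair trade-off: every respondent answers about the same period whenever the survey is completed. The document is dated October 15, 2020, after the June 12 deadline, so only analysis and reporting could still differ.

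On the assumed rates, the early error moves the OR from 6.0 to about 5.8 and prevalence from 10% to 9.9%, and 5% late infections move the OR to 5.5. With 100 participants, chi-square in these cases stays at 7.46 or more, against a critical value of 3.84. These figures rest on even draws and onsets, zero sensitivity before day 14 and chosen illness rates. The true size cannot be computed from the documents.

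An additional restricted analysis could not resolve shifts of this size and would leave the late error in place. What remains is ordinary reporting: when draws took place, and that IgG-positive participants without illness are those with none recorded through May 5. The second point follows from the look-back the plan already states.

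### The survey was sent before the blood test, but no passage states that it had to be submitted before the antibody result was available, or that this was checked

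*Combined protocol and SAP*

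**What the plan says.** All references are to the combined protocol and SAP.

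- **Blinding.** Participant blinding is described as not feasible. The section identifies reporting bias "which may have been affected by knowledge of antibody status" and says that, to reduce it, "the survey was sent in advance of serology testing". It adds that "The research assistants responsible for data collection were blinded to individual serology testing results" and that "participants were advised they could check the results of their serology independently", through Occupational Health.
- **Recruitment and participants.** The electronic survey "was provided, together with an invitation to self-schedule an appointment for SARS-CoV-2 serology testing". "Participation was open between May 6, 2020 and June 5, 2020", and June 12, 2020 was the deadline for finishing both parts. "Only those participants who completed both the survey and serology testing were included in the analyses".
- **Survey and SARS-CoV-2 IgG antibody testing.** Answers are retrospective and cover January 1 to May 5, 2020. The items include COVID-19-like illness, specific symptoms, prior testing and close contacts with confirmed cases.
- **Outcomes and measurement; Statistical Analyses.** The association of IgG with self-reported illness is part of the primary outcome. The χ² test is described in terms of symptoms. Differences in the other survey items, including close contacts, are secondary. No comparison of survey and result dates is described.

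**The concern.** The safeguard concerns dispatch, whereas the bias the plan names depends on submission. A participant could book an early test, look up the result, answer the survey afterwards and still be analysed. Blinding the research assistants does not protect answers that participants give about themselves.

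What is at stake is the survey-based half of the primary outcome. Someone who knows a positive result might relabel a mild illness as COVID-like, and someone who knows a negative result might discount one. Both would raise the odds ratio. Over-reporting by IgG-negative participants would lower it. The illness item is the most open to relabelling. Symptoms and close contacts are less so, although a known positive result could prompt a harder search of memory. Role, training status and commuting are unlikely to be affected. Seroprevalence is a laboratory measure and does not depend on survey answers.

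**Working it through.** **1. Order of events in the text.** The plan states no sample size, effect size or share of late surveys, so there is no figure of its own to reproduce.

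| Question | What the documents state |
|---|---|
| Survey sent before the test? | Yes (Blinding) |
| Survey required before the test or the result? | Not stated |
| Separate, earlier survey deadline? | No; one date for both parts (Recruitment and participants) |
| Result withheld until the survey is in? | Not stated |
| Analysis conditional on order? | Not stated; completing both suffices |
| Submission dates compared with result dates? | Not stated (Statistical Analyses) |

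**2. Calendar.** May 6 to June 12 is 37 days: 30 days to June 5, plus 7 to the deadline. This is the maximum study span. An individual's at-risk interval runs from result available to survey submitted. It is shorter and unknown, because result turnaround is not given.

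**3. Illustration; every input is an assumption.** Let p1 and p0 be true illness reporting in IgG-positives and IgG-negatives, and L the late share.

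- Observed in positives: p1 + (1 − p1) × L × upgrade
- Observed in negatives: p0 − p0 × L × downgrade + (1 − p0) × L × over-report
- OR = odds in positives ÷ odds in negatives

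Cases: (a) upgrade 10%, nothing else; (b) upgrade 30% and downgrade 20%; (c) over-report 10% in negatives, nothing else.

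Example, (b) at L = 0.50 with p1 = 0.40 and p0 = 0.20: positives 0.40 + 0.60 × 0.50 × 0.30 = 0.490; negatives 0.20 − 0.20 × 0.50 × 0.20 = 0.180; OR = (0.490/0.510) ÷ (0.180/0.820) = 4.38.

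| True OR | Case | L = 5% | 10% | 25% | 50% |
|---|---|---|---|---|---|
| 2.67 (40% v 20%) | (a) | 2.70 | 2.73 | 2.84 | 3.02 |
| 2.67 | (b) | 2.80 | 2.95 | 3.42 | 4.38 |
| 2.67 | (c) | 2.60 | 2.54 | 2.36 | 2.11 |
| 1.00 (25% v 25%) | (a) | 1.02 | 1.04 | 1.10 | 1.21 |
| 1.00 | (b) | 1.08 | 1.15 | 1.42 | 1.96 |
| 1.00 | (c) | 0.98 | 0.96 | 0.91 | 0.83 |

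At L = 0 there is no bias. Other assumed inputs give the same pattern: 50% v 20% (true OR 4.00), with upgrade and downgrade both 10%, gives 4.13, 4.34 and 4.71 at L = 10%, 25% and 50%.

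**4. The third factor.** Bias needs late submission, having checked the result, and a changed answer. The formula carries only the first and third. If a share c of late responders checked, L is replaced by L × c. With 50% late and half of them having checked, 0.50 × 0.50 = 0.25, so case (b) gives 3.42 rather than 4.38. The tabulated shifts are therefore upper values unless the switching rates already allow for people who never checked. Late share and switching rate enter only as a product, so neither can be said to dominate.

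**5. Precision lost by restriction.** If exclusions fall proportionally across the 2×2 cells, the standard error grows by 1/√(1 − share excluded): 1.03 at 5%, 1.05 at 10%, 1.15 at 25% and 1.41 at 50%.

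**The case against.** The plan is open about the problem. It says participants could not be blinded, names the bias and claims only to reduce it, not to fix the order for each person. The survey was in hand before any blood draw, the recall window is fixed, and results were to be sought from a separate department. The text is a short past-tense methods account dated October 15, 2020. It does not describe how the survey was administered or how fast results came back, so silence on order is not proof that order was uncontrolled. The χ² test is described in terms of symptoms, which are less open to relabelling than the illness item. The largest odds ratios need late shares and switching rates that nothing in the documents supports.

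Most of this stands, and it limits the size of the point. It does not remove it: none of these features fixes the order of survey and result for a given participant, and a survey answered after the result counts the same as one answered before.

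A reader might infer more than the documents support:

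- *Late surveys occurred, or nothing in the study prevented them.* The documents show only that no passage states an order rule or a check.
- *The reported association is inflated.* Upward bias follows from assuming that answers move toward the known result. Case (c) goes the other way, and the documents do not settle the direction.
- *Results were released only on request.* The text says participants could check them. It does not say this was the only route.

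**Conclusion.** The point holds in a limited form. The plan names a reporting bias in part of its primary outcome and gives a participant-level safeguard tied to dispatch. No passage states that submission before the result was required or verified. Bias in the illness or symptom association, and to a lesser degree the close-contact association, is therefore possible.

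Occurrence, size and direction are undetermined. The illustrative range runs from negligible (2.67 to 2.70–2.73 in case (a) at 5–10% late) to material (4.38 in case (b) at 50% late), with a downward case reaching 2.11. It rests wholly on assumed illness rates, late shares and switching rates. Severity is low: this is a cheap improvement, not a flaw that undermines the study.

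**What to change.** Keep the all-completers analysis as primary and add a check.

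1. From survey submission dates and laboratory dates (assumed to be held), tabulate by IgG status how many surveys were submitted after the blood draw and how many after the result was available.
2. If none followed the result, report that; the point is then closed.
3. Otherwise, repeat the illness, symptom and close-contact associations as a sensitivity analysis restricted to surveys submitted before the result was available. A cut-off at the draw is a stricter option.
4. If the dates are not held, state the limitation.

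The cost is one tabulation and one or two re-runs of existing analyses, with no new data. Three limits should be reported with it:

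- Restriction removes only bias from knowing this study's result. Knowledge from prior SARS-CoV-2 testing remains. Because a result being available is not the same as its being known, the cut-off also drops people who never checked.
- Precision falls by the factors in step 5 of the working, and by more with the draw cut-off. If IgG-positives are few, the loss could be severe; the plan gives no sample size and uses exact logistic regression.
- Early and late responders may differ, so a changed odds ratio is not proof of reporting bias.
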